## 1. INTRODUCTION

### 1.1 BACKGROUND

#### 1.1.1 HUMAN PAPILLOMAVIRUS AND INFECTION

Human papillomaviruses (HPV) are double-stranded DNA viruses with more than 100 genotypes some of which can lead to malignant neoplasia, localized primarily in the anogenital area and aerodigestive tract, in both men and women. HPV types tropic to mucosal tissues are classified into high-risk (HR), based on their potential to cause cancer, and low-risk (LR) causing generally benign lesions. HPV-16 and HPV-18 are the most significant amongst high-risk types since they are responsible for most HPV-caused cancers [1].

HPV-16/18 is involved in about 83% of HPV-associated vulvar HSIL cases in the U.S. [1] and about 72% in Europe [2]. Persistent infection with one or more oncogenic (high-risk) HPV genotypes can lead to the development of precancerous, histologic high grade squamous intraepithelial lesions (HSIL).

HPV causes more cancers than any other virus. In U.S. archival tissues of cancers diagnosed from 1993 to 2005, HPV DNA was detected in 68.8% of vulvar, 90.6% of cervical, 91.1% of anal, 75.0% of vaginal, 70.1% of oropharyngeal, 63.3% of penile, 32.0% of oral cavity, and 20.9% of laryngeal cancers, as well as in 98.8% of cervical cancer in situ (CCIS).

#### 1.1.2 VULVAR CANCER

Vulvar HSIL can lead to vulvar cancer with an estimated 6,020 new cases and 1,150 attributable deaths annually for year 2017 in the United States [4] and about 9,776 new cases in 2015 in Europe [5]. Vulvar cancers consist largely of squamous cell carcinomas and accounts for approximately 5% of all female genital malignancies [6]. Differentiated VIN, which is typically not caused by HPV infection and is more typically found in older women, is more likely to progress to cancer more rapidly than HPV-associated-VIN. The five year overall relative survival for vulvar cancer in the U.S. is 72.1% [4]. Recurrent vulvar cancer occurs in an average of 24% of cases after primary treatment, after surgery with or without radiation [7].

#### 1.1.3 VULVAR INTRAEPITHELIAL NEOPLASIA (VULVAR HSIL)

HPV-associated vulvar intraepithelial neoplasia (VIN) is a chronic (typically persisting for years), premalignant disorder of the vulvar skin that is caused by persistent infection with one or more high-risk genotypes of HPV. Infected cells produce E6 and E7 oncoproteins constitutively, which increases the degradation of cell cycle regulation proteins p53 and pRb, respectively, resulting in unrestricted cell growth and neoplasia. The basis for progression to cancer is, therefore, attributed to the viral proteins E6 and E7. VGX-3100 specifically induces immune responses against E6 and E7, thereby enabling clearance of pre-malignant cells as demonstrated in the Phase 2 study of cervical HSIL [8].

In 2004, the International Society for the Study of Vulvovaginal Disease (ISSVD) replaced the three grade classification system with the current single grade classification for which only high grade VIN (2/3) is classified as VIN [9]. In 2012, the Lower Anogenital Squamous Terminology (LAST) Standardization Project for HPV-associated lesions applied the term high grade squamous intraepithelial lesion (HSIL) to encompass high grade dysplasia [10]. Therefore, for the purpose of this study, the term vulvar HSIL will be used, which encompasses VIN 2 and VIN 3; the term 'vulvar LSIL' will be used to encompass what was previously known as VIN 1.

Once vulvar HSIL has developed, spontaneous regression is rare, likely occurring in only 1.5% to 5% of women [11]. Over time, typically years, vulvar HSIL can progress to invasive cancer of the vulva, e.g. from treated patients, median: 2.4 years in one group and median 13.8 years in another group [12], and from VIN3 patients, mean = 2.5 years, range: 4 – 216 months [13].

Vulvar HSIL remains a significantly unmet medical condition for the following reasons which will be described further: 1) the rate of recurrence of vulvar HSIL under currently used surgical and medical approaches is extremely high, 2) there is a high psychological and physical negative impact of surgery, 3) vulvar HSIL is symptomatic and impacts activities of daily living, 4) prophylactic HPV vaccines have no therapeutic activity against vulvar HSIL and have not achieved universal uptake, leaving a population of susceptible and impacted women, and 5) the early diagnosis of vulvar HSIL is limited to visual inspection with biopsy.

#### 1.1.4 RECURRENT DISEASE WITH CURRENT THERAPEUTIC OPTIONS

There remains an unmet medical need with regard to effective treatment options for vulvar HSIL. Current treatment options show a significant risk of vulvar HSIL recurrence, often requiring multiple, repeat treatments. Progression to vulvar cancer following current vulvar HSIL treatments can also occur within 1 year of treatment and for up to 20 years post treatment. The current treatment options for vulvar HSIL are surgical excision, laser ablation, and off-label medical therapy. The rate of HPV-associated vulvar HSIL recurrence after surgical treatment is high; post-treatment recurrence rates are as high as 45% at three years post-treatment with all currently available treatment regimens [14, 15].

Wide local excision is the 'preferred initial intervention' by ACOG if invasive carcinoma is suspected, and, vulvar biopsy shows vulvar HSIL. If occult invasive disease is not suspected, vulvar HSIL treatment includes surgery: wide local excision, partial vulvectomy, skinning vulvectomy, or simple vulvectomy, laser ablation. Surgical treatments are associated with disruption of normal anatomy and subsequent issues with body image and sexual dysfunction. Medical therapies have been investigated as a means to avoid these negative outcomes. Clinical trials have shown the application of topical imiquimod to be effective however it has not been approved by the U.S. Food and Drug Administration for this indication. Inconsistent treatment efficacy results have been shown with photodynamic therapy, topical cidofovir and topical 5-fluorouracil.

Vulvar HSIL may be followed (with interim observation, but, no intervention) if the patient is young, and, or, if the immune-compromised state is being corrected. Women with pathologic clear margins (no vulvar HSIL) after surgical excision have a lower, yet significant, risk of recurrence compared to women with involved margins. Laser ablation is acceptable treatment for vulvar HSIL when cancer is not suspected, although the risk

of recurrence is slightly higher compared to wide local excision. Laser treatment of vulvar HSIL requires destruction of cells through the entire thickness of the epithelium including hair follicles (in hair-bearing areas of the vulva). In areas without hair, ablation should extend through the dermis. Post-treatment recurrence rates exceed 30% (for all treatment regimens), and is higher with positive excision margins [16].

### 1.1.5 PSYCHOLOGICAL AND PHYSICAL IMPACTS OF CURRENT THERAPEUTIC OPTIONS

Virtually all patients with HPV-related Vulvar HSIL will require treatment, given the low rate of spontaneous resolution. According to the current ACOG & ASCCP guideline for management of VIN, because of the potential for occult invasion and if cancer is suspected (even if biopsy shows vulvar HSIL), the standard treatment of vulvar HSIL is wide local excision (i.e. surgery) [17]. When occult invasion is not a concern, vulvar HSIL can be treated with excision, laser ablation, or topical imiquimod as an off-label medical therapy.

Current treatment options are associated with pain, disfigurement and a recurrence rate as high as 45% at three years post-treatment [16]. Therefore, many patients have a fear of recurrence and progression to cancer [18].

In excisional treatment, patients are advised to rest for two weeks, including delaying return to work for up to one week, and to avoid sexual intercourse for up to 5 weeks. Furthermore, patients are instructed to avoid baths and exercise for a few weeks, and some women are advised to avoid the use of toilet paper and to rinse with warm water instead. During recovery, common effects include pain in urinating and wiping, soreness, difficulty sitting, and feeling tired [19]. In the first week after hospital discharge, common patient-reported symptoms and other effects include swelling, drainage, pain, bleeding, numbness, redness, hardness, burning, pressure, unusual odor, changed skin color, opening of suture, warmth, itching, scarred skin, tiredness (including some feeling of exhaustion), insecurity, feeling of changed body, sexual concerns, anxiety, sadness, changed feeling in self-confidence, and difficulties in partnership [20].

### 1.1.6 IMPACT OF VULVAR HSIL UPON ACTIVITIES OF DAILY LIVING

The presence of vulvar HSIL is frightening and can have long-lasting effects on well-being [19]. The symptoms and signs of vulvar HSIL can be moderate to severe and include painful sexual intercourse, itching or burning, and visible lesions.

In the first week after hospital discharge from surgical excision, common patient-reported impacts on daily life include difficulties sitting, wearing clothes (e.g. underwear, pants), carrying out activities (e.g. climbing stairs, cooking), bowel movements, and urinating [20].

In a study of sexual function and quality of life after excisional treatment, vulvar HSIL patients reported significantly poorer scores in sexual function and quality of life than age-matched healthy women. During the post-treatment follow-up phase of about one year, until given assurance of lesion clearance some patients report the sense that they are in the doctor's office all the time [19].

### 1.1.7 LIMITATIONS OF PROPHYLACTIC HPV VACCINES

Immunization with prophylactic vaccines represents the initial recommended approach within the pediatric and young female populations to avoid later development of HPV-associated vulvar HSIL and subsequent vulvar cancer. The US-licensed prophylactic HPV vaccines are indicated for girls and women ages 9 through 26 years for Gardasil® and Gardasil®9 (Merck & Co. Inc.), and ages 9 through 25 years for Cervarix® (GlaxoSmithKline). The early portions of these age ranges are generally before sexual debut and thus can allow immunologic protection against the anticipated earliest normal exposures to HPV infection. HPV prophylactic vaccination is highly effective and safe, and routine vaccination is recommended for females in the United States starting at age 11 or 12 years [22]. However, these prophylactic vaccines have no therapeutic effect upon existing HPV infection or existing HPV-related intraepithelial neoplasia [23].

### 1.1.8 ENHANCED MONITORING PLAN

An enhanced monitoring plan will be used in this study to address the risk of a potential delay in treatment of vulvar HSIL. The feasibility of this approach was demonstrated in the Phase 2b study of cervical HSIL. Given that vulvar disease progresses slowly to vulvar cancer if untreated, the proposed enhanced monitoring plan is expected to maintain the safety of subjects in this study. First, only Gynecology-Oncologists and Gynecologists who are well experienced in the monitoring and management of vulvar disease will be used as study Investigators. Inclusion into the study will require histologic confirmation of the diagnosis of the vulvar disease as vulvar HSIL, and not carcinoma, by two independent expert pathologists from the PAC (see Section 10.4.2). Women with differentiated VIN, which is more likely to progress faster and is not typically HPV-related is specifically excluded from study entry. By contrast, HPV-associated vulvar HSIL does not progress rapidly, typically taking years to manifest and progress, making enhanced monitoring feasible [24].

Throughout the study, there will be frequent vulvoscopy as well as photographic documentation and analysis of the lesion size (see Section 6.1). Colposcopy will also be performed at Day 0 and during the study given that concurrent disease in the lower genital tract can occur. A Data Safety Monitoring Board will be utilized to review subject safety data and advise on any study-level safety concerns. Investigators always have the option of performing ad hoc vulvar biopsies to rule out suspected disease progression. Additional treatment (e.g., additional excision, ablation, or medical therapy) may be carried out, if deemed necessary according to Investigator judgment.

### 1.1.9 VGX-3100

VGX-3100 encodes HPV-16 E6/E7 and HPV-18 E6/E7 antigens. The plasmids were designed and constructed using proprietary synthetic vaccine (SynCon™) technology. This process involves synthetically deriving consensus genes across multiple strains and optimizing DNA inserts at the genetic level to allow high expression in human cells. Together, VGX-3100 and the CELLECTRA™ device represent an integrated investigational product designed as a non-surgical treatment of HPV-16/18-related cervical HSIL (CIN2, CIN3) via an immune response directed against HPV-16/18. Further information about VGX-3100 is provided in the Investigator's Brochure.

### 1.1.10 ELECTROPORATION

VGX-3100 is delivered using the CELLECTRA™ *in vivo* electroporation (EP) device. EP is a physical method of tissue transfection whereby the generation of short, controlled electrical pulses creates a localized electric field at the injection site of the DNA vaccine which increases cell membrane permeability and improves the transfection of DNA and subsequent immunogenicity [25, 26]. Electroporation increases the uptake of plasmid DNA, thereby enabling increased expression and enhanced vaccine immunogenicity by 10 to 100 fold [27, 28]. This technology has been used for more than three decades by molecular biologists for cell transfection and has demonstrated versatility in use, as shown by its functionality in combination with a range of molecules, tissue types, disease indications, and across species [29].

This study will use the CELLECTRA™ 2000 device which has been used in 26 trials with 3795 doses administered to human subjects as of September 30, 2016 with no significant safety issues identified. Further information about the CELLECTRA™ 2000 device can be found in the Investigator's Brochure and device User Manual.

### 1.1.11 IMIQUIMOD CREAM, 5%

Imiquimod Cream, 5% is a licensed product intended to be used in this study concomitantly with the investigational product and device. Imiquimod Cream, 5% will be centrally sourced, supplied in single-use packets (24 per box), each of which contains 250 mg of the cream, equivalent to 12.5 mg of imiquimod. The product manufacturer is Perrigo, Yeruham 80500, Israel.

### 1.1.12 STUDY RATIONALE

This pilot study is being conducted in a population with vulvar dysplasia using a randomized, open-label design to demonstrate the efficacy of VGX-3100 followed by EP in women with vulvar HSIL associated with HPV-16/18 either alone or in combination imiquimod. The overall aim is to determine if treatment with VGX-3100 could allow women with vulvar HSIL to avoid or minimize surgical treatment procedures. Proof of concept that VGX-3100 can induce resolution of both HPV-associated dysplastic lesions and the underlying HPV-16/18 infection was shown in a Phase 2b study of cervical intraepithelial neoplasia (CIN). The similar underlying pathogenic mechanisms between cervical and vulvar HSIL form the basis of the clinical hypothesis that VGX-3100 could be a non-surgical therapeutic option for the treatment of vulvar HSIL, which is a significantly under met medical condition. A VGX-3100 with imiquimod-administration arm is also included, given the prevalent use of imiquimod as a topical medical treatment of vulvar lesions, to investigate if a more robust immune response is achieved with VGX-3100, to potentially increase regression of vulvar HSIL.

### 1.1.13 DOSE AND REGIMEN RATIONALE FOR VGX-3100

A total dose of 6 mg VGX-3100 DNA has been selected for this study based on previous human experience with VGX-3100, preclinical data with VGX-3100 and other DNA vaccines, and the safety and immunogenicity data generated in the HPV-001, HPV-003, and HPV-101 studies. In HPV-001 trial, the 6 mg dose was delivered IM followed by EP, which showed trends toward higher response rates and magnitudes of IFN-γ ELISpot

responses compared to the low (0.6 mg) and mid-dose (2 mg) cohorts without significant safety issues [30].

#### **1.1.14 RATIONALE FOR IMIQUIMOD**

Imiquimod cream is prescribed for the topical treatment of certain skin growths including external genital and perianal warts. Therefore, imiquimod may be able to be used synergistically with VGX-3100.

Randomized controlled trials have shown that the application of topical imiquimod 5% is effective for the treatment of vulvar HSIL although it is not approved by the US Food and Drug Administration for this purpose. Imiquimod is currently recommended as a non-surgical, off-label treatment option for vulvar dysplasia by the American College of Obstetricians and Gynecologists (ACOG). Published regimens include three times weekly application to affected areas for 12 – 20 weeks, with colposcopic assessment at 4-6 week intervals during treatment [17].

The current study will include an arm to explore whether the efficacy of VGX-3100 is able to be enhanced by concomitant treatment with Imiquimod.

#### **1.1.15 INCLUSION OF WOMAN-PRO, CLINICAL TRIAL VERSION 2.0**

The original WOMAN-PRO (WOMen with vulvAr Neoplasia PRO) was developed by Beate Senn and colleagues [20,31,32] for use following post-surgical intervention. Development of the tool was aligned with the FDA PRO Guidance [33] and included a review of the literature as well as direct patient and expert input. Preliminary measurement properties were assessed in a cross-sectional study. However, despite rigorous development and promising initial measurement properties, gaps in the development and psychometric evaluation exist. To address these gaps, Inovio and collaborators initiated a small qualitative study to confirm the content validity of the tool and support a cross-cultural adaptation of the measure for use in a clinical trial setting of US English and US Spanish speaking subjects. The results of this research is the Clinical Trial of the WOMAN-PRO (2.0) which is utilized in this study.

The WOMAN-PRO Clinical Trial Version 2.0 is a 31 item self-completed patient reported outcome measure designed to assess both physical and psychosocial impacts of VIN. The physical domain is comprised of 15 lesion-related symptoms and includes 5 additional items to measure impact in daily life. Psychosocial constructs are assessment through 11 items that address feelings, thoughts and limitations. Each item is scored using a 4-point Likert scale with higher scores indicating greater difficulty or severity. The recall period is the past week. Details are included in [Section 6.8](#).

#### **1.1.16 POTENTIAL RISKS OF INVESTIGATIONAL PRODUCTS**

Based on the phase 1 and 2 clinical experience, the injection site reactions associated with the IM injection and electroporation are generally mild and limited to a few days in duration at most. The full risk profile for VGX-3100 is described in the Investigator Brochure.

Local skin and application site reactions are the most frequently reported adverse reactions associated with topical imiquimod 5% treatment. Erythema, erosion, excoriation/flaking, edema, induration, ulceration, scabbing, and vesicles have been

reported at the application site [34]. The full risk profile of imiquimod 5% treatment is available in the package insert and prescribing information.

### 1.1.17 POTENTIAL BENEFITS OF STUDY PARTICIPATION

This study has been designed to provide non-surgical treatment with the aim of avoiding the need for surgical excision or laser ablation, which can be disfiguring and have significant associated morbidity. In the absence of complete resolution of vulvar lesions, there would still be potential benefit from a partial response, which would minimize the amount of excisional therapy that may be needed. All currently accepted surgical treatments for VIN are associated with risks inherent with any surgical procedure including anesthesia, post-operative bleeding, infection, or damage to surrounding structures such as the clitoris, urethra, or anus. The other potential benefit is that the response to VGX-3100 is systemic and may clear the underlying HPV infection, which is the root cause of vulvar HSIL. Consequently, there is the potential to reduce the risk of recurrent disease.

## 2. HYPOTHESIS AND STUDY OBJECTIVES

Four 6 mg doses of VGX-3100 (DNA plasmids encoding E6 and E7 proteins of HPV-16 and HPV-18) delivered intramuscularly (IM) followed by electroporation (EP) with CELLECTRA™ 2000 alone or in combination with imiquimod to adult women with histologically confirmed vulvar HSIL associated with HPV-16 and/or HPV-18 (HPV-16/18), will result in a higher percentage of women with regression of HSIL of the vulva based on histology (i.e. biopsies or excisional treatment) and virologic clearance of HPV-16/18 from vulvar tissue compared with historical control.

### 2.1 PRIMARY OBJECTIVE AND ENDPOINT

Objective	Endpoint
Determine the efficacy of four doses of VGX-3100, alone or in combination with imiquimod, with respect to combined histopathologic regression of vulvar HSIL and virologic clearance of HPV-16/18 in vulvar tissue	Proportion of subjects with no histologic evidence of vulvar HSIL and no evidence of HPV-16/18 at Week 48 in vulvar tissue samples (i.e. collected via biopsy or excisional treatment).

## 2.2 SECONDARY OBJECTIVES AND ASSOCIATED ENDPOINTS

Secondary Objectives	Associated Secondary Endpoints
1. Evaluate the safety and tolerability of VGX-3100 delivered IM followed by EP with CELLECTRA™ 2000, alone or in combination with imiquimod	1a. Local and systemic events for 7 days following each dose as noted in the Participant Diary. 1b. All adverse events including SAEs, SUSARs, UADEs, and other unexpected AEs for the duration of the study (through Week 100 visit)
2. Determine the efficacy of four doses of VGX-3100, alone or in combination with imiquimod, as measured by histologic regression of vulvar HSIL	2. Proportion of subjects with no evidence of vulvar HSIL on histology (i.e. biopsies or excisional treatment) at Week 48 visit
3. Determine the efficacy of four doses of VGX-3100, alone or in combination with imiquimod, as measured by virologic clearance of HPV-16/18 in vulvar tissue	3. Proportion of subjects with no evidence of HPV-16/18 in vulvar tissue samples at Week 48 visit
4. Determine the efficacy of VGX-3100 , alone or in combination with imiquimod, as measured by histologic regression of vulvar HSIL to normal tissue	4. Proportion of subjects with no evidence of vulvar HSIL, no evidence of vulvar LSIL (VIN1), and no evidence of condyloma on histology (i.e. biopsies or excisional treatment) at the Week 48 visit
5. Determine the efficacy of four doses of VGX-3100 , alone or in combination with imiquimod, as measured by non-progression of vulvar HSIL to vulvar cancer as determined by histology	5. Proportion of subjects with no progression of vulvar HSIL to vulvar cancer from baseline to Week 48 visit
6. Determine the efficacy of VGX-3100, alone or in combination with imiquimod, as measured by reduction in the surface area of the qualifying vulvar lesion(s)	6. Percent reduction in the cumulative surface area of the acetowhite vulvar lesion(s) as determined by the quantitative analysis of standardized pre-biopsy photographic imaging of the qualifying  lesion (s) at Week 48, 74 and 96 compared to baseline  . Results will be classified as: no clinically significant lesion resolution (reduction in lesion size of 0-25%), partial lesion area resolution (>25% and <100% reduction), and complete lesion resolution (no visible lesion).
7. Describe the humoral and cellular immune response of VGX-3100 administered alone or in combination with imiquimod, post dose 3, post dose 4, and after additional dosing	7a. Levels of serum anti-HPV-16 and anti-HPV-18 antibody concentrations at baseline, Weeks 15, 27, 48, 74, and 96 visits 7b. Interferon-γ ELISpot response magnitudes at baseline and Weeks 15, 27, 48, 74 and 96 visits 7c. Flow Cytometry response magnitudes at baseline and Week 27 visits

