### 3.2.1 DEFINITION OF RESPONDER AND NON-RESPONDER

A treatment responder is defined as a subject with no histologic evidence of vulvar HSIL and no evidence of HPV-16 or HPV-18 in vulvar tissue at evaluation and who did not receive any non-study related treatment for vulvar HSIL. A treatment non-responder is a subject with histologic evidence of vulvar HSIL or vulvar carcinoma at evaluation, or a subject with evidence of HPV-16/18 at evaluation, or a subject who received non-study related treatment for vulvar HSIL. Any case of histologically confirmed progression is considered a non-responder. Progression is defined as advancement to carcinoma by histology according to the PAC.

Responder and non-responder definitions (Table 3) take into account both histopathologic regression of vulvar HSIL and virologic (HPV-16/18) clearance from tissue samples since HPV persistence is an important factor in the clinical progression of HSIL.

Table 3: Definition of Responder and Non-responder	
Responder	Non-Responder
Subject with no histologic evidence of vulvar HSIL AND Subject with no evidence of HPV-16 or HPV-18 in vulvar tissue at evaluation AND Subject who did not receive any non-study related treatment for vulvar HSIL	Subject with histologic evidence of vulvar HSIL or vulvar carcinoma at evaluation OR Subject with evidence of HPV-16 or HPV-18 in vulvar tissue at evaluation OR Subject who received non-study related treatment for vulvar HSIL

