 Throughout this protocol high grade disease (previously known as VIN2 or VIN3) is referred to as vulvar HSIL according to the 2015 International Society for the Study of Vulvovaginal Disease (ISSVD) Terminology of Vulvar Squamous Intraepithelial Lesions and 2012 consensus recommendation on Lower Anogenital Squamous Terminology (LAST) from the American Society of Colposcopy and Cervical Pathology (ASCCP) and the College of American Pathologists (CAP).

 Inclusive of administration on day of dosing.

 No evidence of vulvar HSIL is defined as normal tissue or vulvar LSIL (VIN 1) or condyloma

 A treatment responder is defined as a subject with no histologic evidence of vulvar HSIL and no evidence of HPV-16 or HPV-18 in vulvar tissue at evaluation and who did not receive any non-study related treatment for vulvar HSIL. A treatment non-responder is defined as a subject with histologic evidence of vulvar HSIL, or vulvar carcinoma at evaluation, or a subject with evidence of HPV-16/18 in vulvar tissue at evaluation, or a subject who received non-study related treatment for vulvar HSIL.

Secondary Objectives	Associated Secondary Endpoints
1. Evaluate the safety and tolerability of VGX-3100 delivered IM followed by EP with CELLECTRA™ 2000, alone or in combination with imiquimod	1a. Local and systemic events for 7 days following each dose as noted in the Participant Diary. 1b. All adverse events including SAEs, SUSARs, UADEs, and other unexpected AEs for the duration of the study (through Week 100 visit)
2. Determine the efficacy of four doses of VGX-3100, alone or in combination with imiquimod, as measured by histologic regression of vulvar HSIL	2. Proportion of subjects with no evidence of vulvar HSIL  on histology (i.e. biopsies or excisional treatment) at Week 48 visit
3. Determine the efficacy of four doses of VGX-3100, alone or in combination with imiquimod, as measured by virologic clearance of HPV-16/18 in vulvar tissue	3. Proportion of subjects with no evidence of HPV-16/18  in vulvar tissue samples at Week 48 visit

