**Figure 4: Evaluation process at Week 100**

In the event of worsening disease at any time (i.e., Subgroup E – any increase in lesion area from baseline or worsening to cancer), the subject will receive surgical treatment per the Investigator's judgment and will continue on study through Week 100 with vulvoscopy, but without further study treatment or biopsy. If at any time in the study carcinoma is discovered, subjects will receive surgical treatment, and be discontinued from study treatment. The event will be reported as an SAE per section 7.1.4. If wide excision is required, the sample obtained will be sent to the PAC for evaluation.

Definition of Responder and Non-responder: Responder and non-responder definitions (Table 3) take into account both histopathologic regression of vulvar HSIL and virologic (HPV-16/18) clearance from tissue samples since HPV persistence is an important factor in the clinical progression of HSIL. A treatment responder is defined as a subject with no histologic evidence of vulvar HSIL and no evidence of HPV-16 or HPV-18 in vulvar tissue at evaluation and who did not receive any non-study related treatment for vulvar HSIL. A treatment non-responder is a subject with histologic evidence of vulvar HSIL or vulvar carcinoma at evaluation, or a subject with evidence of HPV-16/18 at evaluation, or a subject who received non-study related treatment for vulvar HSIL. Any case of histologically confirmed progression from HSIL to carcinoma is considered a non-responder.

Safety Assessment: Subjects will be monitored for:

- 1) Local and systemic events for 7 days following each VGX-3100 dose as noted in the Participant Diary
- 2) All adverse events including SAEs, SUSARs, UADEs, and other unexpected AEs for the duration of the study.

All subjects will be followed for 100 weeks.

Data Safety & Monitoring Board (DSMB): The DSMB will meet quarterly to review safety data and tissue regression and viral clearance results. The DSMB will be charged with advising the Sponsor if there appears to be a safety issue. No formal interim analysis is planned. The following stopping rules will be applied:

- If at any time during the study one-third (1/3) or more of the subjects experience an Adverse Event of Special Interest (AESI), further enrollment and study treatment will be halted immediately until a thorough investigation has been conducted by the Medical Monitor, Principal Investigator (PI) for the trial, and the DSMB.

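### Secondary endpoints 2, 3 and 4 omit the non-study-treatment condition of the primary endpoint, so a woman treated outside the study who is clear at Week 48 fails the primary but succeeds on its components

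*Protocol*

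**What the plan says.** The protocol file holds successive versions. Version 2.1 is the latest, but the part shown ends in Section 3, so Sections 3.2, 3.2.1, 4.3.2, 6 and 8 are cited here from version 2.0.

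**Primary endpoint.** In the version 2.1 synopsis the primary endpoint carries footnote 4. Its list of non-responders ends with "or a subject who received non-study related treatment for vulvar HSIL". The responder definition in the synopsis repeats the condition: a responder is one "who did not receive any non-study related treatment for vulvar HSIL". Table 3 in Section 3.2.1 (version 2.0) sets it as the third requirement, "AND Subject who did not receive any non-study related treatment for vulvar HSIL".

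**Secondary endpoints.** In Section 2.2, endpoint 2 is the absence of HSIL "on histology (i.e. biopsies or excisional treatment) at Week 48 visit". Endpoint 3 is the absence of HPV-16/18 "in vulvar tissue samples at Week 48 visit". Endpoint 4 is the absence of HSIL, LSIL and condyloma "on histology (i.e. biopsies or excisional treatment) at the Week 48 visit". Footnote 5 fixes which histology grades count and footnote 6 says that clearance means a negative PCR. Neither mentions other treatment, and none of the three endpoints carries footnote 4.

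**Treatment outside the study.** Section 1.1.8 says: "Additional treatment (e.g., additional excision, ablation, or medical therapy) may be carried out, if deemed necessary according to Investigator judgment".

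**The concern.** Histologic regression and viral clearance are the two tissue components of the composite primary endpoint, and the objectives behind endpoints 2 to 4 present them as efficacy of VGX-3100. If the composite treats outside therapy as failure and the components do not, a woman can meet both components and still fail the composite, with her clear tissue credited to the vaccine. Section 1.1.14 itself reports that topical imiquimod is effective in vulvar HSIL, so the misattribution is plausible, above all in the arm given VGX-3100 alone. At stake are the point estimates and confidence intervals for regression, clearance and regression to normal.

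**Working it through.** **The plan's own figure.** Section 8.3 (version 2.0) gives 36 subjects in a 2:1 ratio, true rates of 20% and 28% against 2%, one-sided 0.025 per arm, 80% power and 90% evaluable. With an exact one-sample binomial test, the smallest evaluable numbers that reach 80% are:

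- VGX-3100 alone: n = 21, at least 3 responders needed, power 82.1% (n = 20 gives 79.4%). 21/0.9 = 23.3, rounded up to 24.
- VGX-3100 plus imiquimod: n = 10, at least 2 responders needed, power 81.7% (n = 9 gives 76.6%). 10/0.9 = 11.1, rounded up to 12.

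24 + 12 = 36, so the sample size reproduces. This point does not touch it.

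**Definitions side by side.**

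| Outcome at Week 48 | Tissue condition | Condition on non-study treatment |
|---|---|---|
| Primary | no HSIL and no HPV-16/18 | yes (footnote 4, responder definition, Table 3) |
| Secondary 2 | no HSIL | none |
| Secondary 3 | no HPV-16/18 by PCR | none |
| Secondary 4 | no HSIL, LSIL or condyloma | none |
| Exploratory 5 (sites other than the vulva) | HPV-16/18 cleared | yes (clearance after surgery does not count) |

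The last row shows that the protocol writes such a restriction into an endpoint where it wants one.

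**Does Section 8.9 supply the rule?** It says the secondary binary endpoints are analysed like the primary hypothesis but without p-values. That carries over the exact Clopper-Pearson interval. It does not redefine who counts as a success.

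**What happens to a woman treated outside the study before Week 48.**

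1. She has medical therapy, ablation or excision under Section 1.1.8, without falling into a group that stops biopsies. The Schedule of Events still has her biopsied at Week 48, and Table 2 (version 2.0) requires the biopsy even when no acetowhite lesion is seen. If the tissue is clear, she is a primary non-responder and a success on endpoints 2 and 3, and on 4 if LSIL and condyloma are also absent.
2. She has surgery for worsening disease. The synopsis keeps her on study but with no further biopsy. Section 8.4 admits to the mITT population only subjects who have the endpoint in question, and Section 8.11.6 imputes nothing. She leaves the denominator of endpoints 2 to 4, whereas the responder definition makes her a non-responder for the primary.

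**Size.** Evaluable numbers: 24 × 0.9 = 21.6, about 22; 12 × 0.9 = 10.8, about 11. The protocol gives no rate of outside treatment, so one such woman per arm is assumed for illustration.

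Route 1, one failure becomes a success: 1/22 = 4.5 points and 1/11 = 9.1 points. With exact 95% intervals:

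| Arm | She counts as failure | She counts as success |
|---|---|---|
| VGX-3100, near the planned composite rate | 4/22 = 18.2% (5.2 to 40.3) | 5/22 = 22.7% (7.8 to 45.4) |
| VGX-3100, low count | 2/22 = 9.1% (1.1 to 29.2) | 3/22 = 13.6% (2.9 to 34.9) |
| Plus imiquimod, near the planned composite rate | 3/11 = 27.3% (6.0 to 61.0) | 4/11 = 36.4% (10.9 to 69.2) |
| Plus imiquimod, low count | 1/11 = 9.1% (0.2 to 41.3) | 2/11 = 18.2% (2.3 to 51.8) |

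At the low counts one woman moves the lower limit across 2%. That value is the reference for the primary endpoint; none is set for endpoints 2 to 4.

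Route 2, she leaves the denominator: 4/22 = 18.2% becomes 4/21 = 19.0% (+0.9 points), and 3/11 = 27.3% becomes 3/10 = 30.0% (+2.7 points).

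**The case against.** The strongest reply is that the rule belongs to the responder definition and was never meant to be repeated in each endpoint. Section 2.1 states the primary endpoint without it too, so its absence from Section 2.2 proves little. That is fair as to intent, but it does not close the gap. In the synopsis, footnote 4 hangs on the primary endpoint only, and endpoints 2 to 4 do not speak of responders. Nor could the responder definition simply be read into them: it requires both tissue conditions, so applying it to endpoint 2 would turn regression back into the composite.

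A second reply is that observed tissue status is a legitimate outcome whatever treatment preceded it, and that the protocol never promises that the components add up to the composite. As a description of tissue this stands. As a measure of the efficacy of VGX-3100, which is how the objectives are worded, it does not.

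A third reply is that the analysis plan, not shown, could settle this. It could, but the protocol defines these endpoints itself and fixes the rule for the composite and not for its parts.

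Some stronger readings are not supported:

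- A reader might infer that every woman treated outside the study is counted as a regression. She is not. Surgery for worsening disease, a finding of carcinoma (Section 7.1.4) and loss of eligibility (Section 4.3.2) all end biopsies, so these women would normally have no Week 48 result.
- A reader might take the mention of excision in endpoints 2 and 4 as the fault. The primary endpoint has a matching parenthesis, and Section 6.2.10 (version 2.0) offers excision at Week 48 as a study procedure.
- A reader might infer an inflated type I error. Endpoints 2 to 4 have no p-values.

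**Conclusion.** The point holds in a narrow form. Endpoints 2, 3 and 4, followed literally, credit VGX-3100 with clear tissue in a woman who had other treatment and was still biopsied at Week 48, and they drop a woman operated on for worsening disease where the primary rule would count her as a non-responder. Both effects run in the favourable direction.

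The first is worth 4.5 points per woman with VGX-3100 alone and 9.1 points with imiquimod; the second about 0.9 and 2.7 points near the planned composite rates. These sizes assume about 22 and 11 evaluable women. How many women would be affected is not stated and may be none. The primary test, its power and the sample size are unaffected. This is a cheap improvement to the plan, not a flaw in its main conclusion.

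**What to change.** Add one condition to the definitions of secondary endpoints 2, 3 and 4, in the synopsis and in Section 2.2: a subject who received non-study treatment for vulvar HSIL between the first dose and the Week 48 sample is counted as not regressed (endpoints 2 and 4) or not cleared (endpoint 3), and stays in the mITT denominator even if no Week 48 tissue exists. State that excision done as the Week 48 study procedure is not non-study treatment.

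Leave footnotes 5 and 6 alone; they define a histology grade and a PCR result, and treatment history does not belong there. The mITT wording in Section 8.4 needs a matching clause, because otherwise the women without tissue would still drop out.

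The cost is wording. Section 6.15 already has medications and procedures recorded on the case report form, so no new data are needed. No treatment, visit, sample size or primary analysis changes. The regression and clearance rates may come out slightly less favourable. If the analysis plan already contains such a rule, the protocol text should be brought into line with it.
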